6. STUDY DEVICES

Blood glucose monitor. Telcare Verizon blood glucose meter (BioTelemetry, Inc, Malvern, PA). *Wireless medication adherence device.* WisePill Dispenser Int 3G (WisePill Technologies, Western Cape, South

Africa). *Cellphone*. Participants not owning a cell phone received an option of two different types of cell phones, a BLU Jenny (Doral, Florida) or an LG Expression with qwerty keyboard (Englewood Cliffs, New Jersey). Wireless service will be provided by U.S. Mobile with unlimited text and voice plans for the duration of the intervention. Data plans will not be provided to any study participants.

7. STUDY SCHEDULE

Intervention assignments are described above. The follow-up periods at months 6 and 12 were chosen to assess immediate and longer-term impact of the intervention, respectively.

- *~1 week prior to Baseline Visit*: EHR Screening, Telephone Screening
- *Baseline Visit*: Informed Consent, Randomization, Brief diabetes education session to be delivered, Labs, blood pressure (BP) and anthropometric data to be obtained, Self-report surveys to be collected
- *Months 1-6*: Delivery of text messages all groups, automated (group 2) or telephonic feedback (group 3)
- *Month 6*: Labs, BP and anthropometric data to be obtained, Self-report surveys to be collected
- *Month12*: Labs, BP and anthropometric data to be obtained, Self-report surveys to be collected

7. ASSESSMENTS AND DATA COLLECTION

Clinical Measures:

- Clinical specimens (blood draws), HbA1C and lipid assays
- Physical measures (blood pressure, weight, height)

As part of Aim 1, we will evaluate key clinical indicators of diabetes control by measuring HbA1c, lipids, and BP. At baseline, month-6, and month-12 assessments, blood will be drawn at the clinic by existing Neighborhood Healthcare laboratory staff following a 12-hour fast and processed by Quest Diagnostics Inc., which adheres to all guidelines set forth by the College of American Pathologists. The primary outcome of HbA1c will be assayed by Immunoturbidimetry (Integra 800, Roche). Research assistants will measure BP and anthropometrics using standardized protocols and instrumentation.

Self-Reported Measures and EHR Data Extraction:

- Participant responses to survey instruments
- Records of demographics, comorbidities, and medications extracted from EHRs;

For Aim 2, participants will complete self-report measures of patient-provider communication, and adherence to medication and other diabetes self-management behaviors (dietary intake, physical activity, blood glucose monitoring) at all 3 time-points. Via self-report we will also assess demographic

and health related factors (including medication use) for screening and sample description purposes, and the fit of the overall theoretical model. Patient EHRs will also be reviewed for patient information (i.e., demographics, comorbidities, and medications).

Patient Focus Groups:

As part of the Process Evaluation, 20 participants from the DD-Me condition [split evenly between automated messaging (n=10) and MA-delivered (n=10)] will be invited to key informant interviews to share their experiences with the intervention. Focus group participants must be willing to provide informed consent; available for scheduled focus group/s; and speak Spanish or English. We will not conduct focus groups with Dulce Digital participants as a process evaluation has already been conducted as part of our original RCT.

Electronic health records abstraction:

Demographic and other data are extracted from the EHR for each participant upon enrollment, and clinical and health service utilization data is abstracted for 12 months from each patient's unique enrollment date from all laboratory and ambulatory clinic sites. Standard of care laboratory or anthropometric values resulted in the EHR within the qualifying assessment window will be used for outcome analysis purposes for any participants with missed follow up visits to enhance data completeness. The Scripps Health IRB approval provides permission to audit the EHR for patient identification and outcome analysis purposes.

8. DATA TRACKING

All data are tracked in a Research Electronic Data Capture (REDCap) database and reviewed on a regular basis by supervising research staff. Intervention fidelity forms are used to track the frequency, duration, and content of all telephone outreach to participants, including blood glucose triage and “no (EMA, blood glucose, or Wisepill) data” calls for all participants; and weekly MA Health Coach feedback calls for the DD-Me telephonic Health Coach group. The CYCORE system actively tracks the content and date/time of delivery or receipt of outgoing core content, EMA items, and feedback messages, as well as participants’ responses to EMA items. CYCORE reports are reviewed on a regular basis to ensure that intervention content is delivered as designed; any deviations from protocol or temporary system outages are tracked in REDCap.

9. CONFIDENTIALITY AND DATA ACCESSIBILITY

Confidentiality will be protected by identifying all data forms with a participant ID number, which will be linked to participant identifiable information only on a master list, stored in password protected form on a password protected computer at both primary performance sites, separate from any other study data, and available only to the study PIs, project managers, and other trained research personnel working under the PIs’ supervision if necessary for participant contact, tracking, or follow-up purposes. In general, the trial will take every possible precaution to protect data and ensure that confidentiality is protected both within and across performance sites, via use of ID numbers, safe transport, and other IRB approved procedures. All procedures will be discussed with clinic staff prior to implementation and will be reviewed and approved by the Scripps, SDSU, and UC San Diego IRBs.

Access to individually identifiable private information about the participants will be available only to MPIs [name] and [name] and trained research staff (e.g., project managers) working under their supervision who require this information for a specific purpose. All participant information and data will be de-identified (identified by participant number only). In all cases where data transfer between sites is required, data will be directly transferred from site to site (without stops, excepting emergency) and will be transported in de-identified form, separated from consent forms or other identifying information, and carried in a locked storage box.

8. RETENTION STRATEGIES.

The research team has gained substantial experience with approaches to minimizing attrition through previous efforts. These lessons learned will be applied to maintain the cohort in the proposed study. All participants will receive cohort maintenance postcards at interim study points and reminder postcards prior to each assessment appointment, and will be contacted and rescheduled if an appointment is missed.

Participant Compensation:

Monetary compensation (\$50, \$25, \$40 gift cards for baseline/initial visit, month-6 and month-12, respectively) for time and effort rendered will be offered to all participants following each assessment visit.

Staff Skill:

All research staff will be carefully trained in research protocols and interviewing methods including the process of developing rapport and maintaining a friendly but professional interaction style to ensure that participants have a positive experience with the study.

9. STUDY OVERSIGHT

Collaborating Sites and Plan:

Performance sites include Scripps Whittier Diabetes Institute (SWDI) of Scripps Health (MPI [name]), SDSU (MPI [name]), and UC San Diego (Co-Investigator [name]). In addition, patient recruitment, assessment, and intervention activities will take place at a collaborating FQHC. The study investigators will work with clinic leadership, providers, and staff to optimize plans for patient identification, data collection, and study implementation, including collaboration in developing safety and protocols and staff training. Twice monthly research meetings (or more often as needed) involving the study PIs and all central study staff across both sites will maintain consistent processes and communication. All research staff will be centrally trained and supervised by the study PIs.

Oversight of Clinical Outcomes and Intervention:

SWDI will have primary oversight for Aim 1 (clinical outcomes), cohort identification process via EHR, and interventionist (nurse, MA) training and support, and will also act as the primary liaison to the clinic sites and stakeholders groups. A Project Manager will be housed at Scripps to oversee patient identification, EHR and (overall) implementation of the intervention and staff trainings.

Oversight of Self-Reported Outcomes:

SDSU (with appropriate registration volunteer staff as required) will have primary oversight for the patient reported outcomes Aim (2). MPI [name] (SDSU) will also oversee the overall program evaluation, in close collaboration with Co-I [name] (Scripps), including conducting patient focus groups and obtaining nurse, MA, and other provider input regarding the intervention, and database development, data entry, data verification, and overseeing data analysis in collaboration with the study statistician. A Project Manager will be employed at SDSU to oversee and contribute to the patient reported assessment outcome and overall program evaluation.

Oversight of CYCORE System:

Co-Investigator [name] (UC San Diego) will oversee the development and maintenance of the CYCORE (CYberinfrastructure to support COmparative effectiveness REsearch); a secure, scalable and extensible platform with the ability to support adaptive or dynamic mHealth interventions) system and study technologies, and a Project Manager will coordinate development and implementation of the CYCORE system. The CYCORE system will be responsible for the programming of text messages (DD-Me and Dulce Digital) and adaptive feedback/goal-setting (DD-Me only). For a detailed description of the CYCORE system please see below:

"CYCORE (CYberinfrastructure to support COmparative effectiveness REsearch) is a secure, scalable and extensible platform with the ability to support adaptive or dynamic mHealth interventions. With CYCORE, participants take daily measurements related to health parameters of interest [in early use cases, BP, pulse, and weight]. Through mobile phone based self-report, called EMA, researchers capture information on other indicators of interest from participants (e.g., adherence, other health behaviors, emotional well-being). The mobile phone or other Internet-connected device sends the data to CYCORE's back-end services. Clinicians can monitor these data daily to determine the need for patient outreach. CYCORE has been extremely well received by patients and their support persons. Finally, CYCORE is device and sensor agnostic and can be readily adapted to the DD-Me project. In particular it can handle both inbound data capture from the glucose and medication monitors, and support the logic behind the text message-based EMA and interactive communication (i.e., personalized feedback and goal-setting) with study participants. It has a secure HIPAA compliant database that facilitates data visualization and analysis."

Statistical Analysis Plan

Study Aims

Primary Aim

To compare the effectiveness of DD-Me versus Dulce Digital in improving diabetes clinical control [HbA1c, primary outcome], low-density lipoprotein cholesterol (LDL-c), and systolic blood pressure (SBP) over 12 months.

Secondary Aim

To compare the effectiveness of Dulce Digital versus Dulce Digital Me (Automated and Telephonic) in improving patient reported outcomes (patient adherence, diabetes distress, patient-provider communication over 12 months.

Statistical Methods

Power and Sample Size

This study will enroll $N = 414$ men and women allocated equally to the three groups. RMASS2 was used to estimate the sample size needed to detect statistically significant differences between any of the 3 groups: (a) Dulce Digital, (b) DD-Me (automated delivery), and (c) DD-Me (telephonic MA delivery). For HbA1c, the study primary outcome, a clinically meaningful change of 0.5% with a 1.3% standard deviation was used to determine power. To transform this estimate into an effect size ($d=.33$), standard deviations (SD) from prior studies in the same and similar populations were used. To determine the minimum sample size necessary, assumptions included: (1) An alpha level of .05 and a power level of .80; (2) a missing data rate of 15% at each time-point or a 30% missing data rate overall, and (3) a stationary autoregressive structure (lag 1) for the variance-covariance matrix of the repeated measures, using an autocorrelation value of .45. Given these assumptions and the estimated effect size from above, 414 participants are needed at baseline (i.e., $n=138$ in each of the 3 groups). Although power analyses used HbA1c as the primary outcome, $N=414$ at baseline is adequate to detect a small-to-medium effect size for all physiological and patient-reported outcomes, given a missing data rate of 30% over the course of the study. Allowing for up to 30% attrition, the minimum number of participants required to be retained at 12-months follow-up to ensure adequate power for statistical analysis is 290.

Analytic Plan

All analytic strategies will follow published standards, including intent to treat principles. Preliminary data screening and cleaning will require examination of distributions for normality, outliers, and missing data patterns at both the uni- and multi-variate level. Preliminary inferential statistical testing and effect size consultation will be used to determine if random assignment has resulted in statistical equivalence between groups. Significant covariates will be added to adjust for nonequivalence. Or variables related to missing data Multilevel models using full information maximum likelihood estimation will be conducted to examine changes in the target outcomes for each Aim. Analyses will include the between-subjects factor treatment group and the within-subjects factor time. The cross-level group by time interaction effect will be of primary interest. Within groups changes will also be examined to evaluate

the clinical and statistical significance of relative change. Outcomes assessment will follow the intention-to-treat principle; each participant will be included in between-group comparisons regardless of adherence level and based solely on randomization assignment.

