5. INTERVENTION

5.a. Dulce Digital:

Practical barriers (e.g., work, caregiving, transportation) limit the reach of traditional or face-to-face DSME programs for underserved, at-risk patients. mHealth technologies have the potential to circumvent some of these obstacles. Recently we developed Dulce Digital (DD), which included culturally-tailored and health literacy-sensitive educational and supportive text messages [i.e., short message service (SMS)], combined with patient monitoring and transmission of blood glucose values. Dulce Digital participants received text messages derived from the Project Dulce DSME curriculum, medication reminders, and blood glucose monitoring prompts. As a “static” intervention, all Dulce Digital participants received the same content and dosage of messages (2-3 messages daily initially, with frequency tapered over 6 months). A care-team nurse monitored transmitted glucose values, assessed possible reasons for high-risk values, and encouraged follow up with the primary care provider as needed. In a recent RCT of N=126 Hispanic patients with poorly controlled T2DM ($\text{HbA1c} \geq 8\%$), Dulce Digital led to improved glycemic control across 6 months, relative to usual care [HbA1c mean $\Delta = -1.0\%$ vs. -0.2% , $p<.05$]. Our process evaluation indicated that DD was both feasible and acceptable; however, patients expressed a preference for intervention content tailored to their individual self-management needs and behavioral progress (i.e., an “adaptive” intervention).

Participants in this group receive the original DD, culturally and health literacy-appropriate text messages between baseline and six months (“Core Content”). Over this same period, participants are encouraged to regularly check glucose using a cellular-enabled monitor (“Remote Glucose Monitoring”), manage their oral medication(s) monitor their medication taking using the cellular-enabled pillbox (“Remote Medication Adherence Monitoring”) and respond to ecological momentary assessment (“EMA”) questions about health behaviors and well-being via text message.

5b. Dulce Digital Me (DD-Me):

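### The SAP's power inputs do not agree: 0.5% over an SD of 1.3% gives d = .385, not the stated .33, and no SD that yields .33 is given

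*Combined protocol and SAP*

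**What the plan says.** All the inputs are in the SAP, Power and Sample Size. For HbA1c, the primary outcome, "a clinically meaningful change of 0.5% with a 1.3% standard deviation was used to determine power". The next sentence reads: "To transform this estimate into an effect size ($d=.33$), standard deviations (SD) from prior studies in the same and similar populations were used". No value is given for those SDs.

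The other assumptions are "An alpha level of .05 and a power level of .80", "a missing data rate of 15% at each time-point or a 30% missing data rate overall", and "a stationary autoregressive structure (lag 1) for the variance-covariance matrix of the repeated measures, using an autocorrelation value of .45". The section then concludes that "Given these assumptions and the estimated effect size from above, 414 participants are needed at baseline", which is 138 in each of three groups.

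The one prior trial described, in protocol section 5.a (Dulce Digital), reports that "Dulce Digital led to improved glycemic control across 6 months, relative to usual care". It gives mean changes in HbA1c of -1.0% and -0.2%, without an SD.

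**The concern.** Two adjacent sentences give a difference, an SD and a standardised effect size that do not fit together. The second sentence presents d = .33 as a transformation of the estimate in the first, and the stated inputs do not produce it.

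The effect size is the input on which 414 rests. If the difference and SD are right, the trial has more power for a 0.5% difference than the 80% claimed. If the SD is really near 1.5% and .33 was entered, the sample size matches and only the printed 1.3% is wrong. If .385 was entered while the SD is really near 1.5%, power for 0.5% is below 80%. The text points to .33 as the value entered, but the plan does not let a reader confirm it.

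**Working it through.** **Inputs** (SAP, Power and Sample Size): difference 0.5%, SD 1.3%, stated d = .33, alpha .05, power .80, AR(1) correlation .45, missing data 15% per time-point or 30% overall, 138 per group. Sidedness, time contrast and the exact retention pattern are not stated. Two-sided testing is assumed below.

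**1. Reproduce d.** d = difference / SD = 0.5/1.3 = .3846. The plan prints .33, so it is not reproduced.

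**2. What .33 would require.**
- SD = 0.5/.33 = 1.515%, and 1.515/1.3 = 1.17, about 17% larger.
- Or difference = .33 × 1.3 = 0.43%.

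**3. Rounding.**
- An SD between 1.25% and 1.35% gives d from 0.5/1.25 = .400 to 0.5/1.35 = .370.
- A d between .325 and .335 needs an SD from 0.5/.335 = 1.49% to 0.5/.325 = 1.54%.

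The two ranges do not meet.

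**4. Levels or change?** Take 1.3% as the SD of levels and apply the stated correlation, so that SD of change = 1.3 × √(2(1 − r)).
- Baseline to month 6, r = .45: SD 1.363, d = .367.
- Baseline to month 12, r = .45² = .2025: SD 1.642, d = .305.

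Baseline-adjusted SDs, 1.3 × √(1 − r²), are 1.161 (d = .431) and 1.273 (d = .393). No single visit gives .33.

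**5. Effect on sample size.** Under any fixed contrast n is proportional to 1/d²: (.33/.3846)² = .736, so .385 needs about 26% fewer patients. In a simple two-group comparison, n per group = 2(1.960 + .842)²/d² = 144.1, so 145, at .33; and 106.1, so 107, at .385.

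**6. Does N reveal which d was entered?** RMASS2's settings are not given, so a standard repeated-measures formula stands in:

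n = 2(1.960 + .842)² V/(d L)², with V = Σ c_i c_j × .45^|i−j| / √(r_i r_j).

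Here c is the contrast over baseline, month 6 and month 12, r is the proportion observed at each visit, and L = 1 in both cases below.

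| Assumed contrast and retention | V | n at .33 | n at .385 | Power at 138, d = .33 | Power at 138, d = .385 |
|---|---|---|---|---|---|
| Mean of months 6 and 12: c = (0, .5, .5), r = (1, .85, .70) | .943 | 135.9 | 100.1 | .806 | .908 |
| Baseline to mean of months 6 and 12: c = (−1, .5, .5), r = .85 throughout | 1.262 | 181.9 | 133.9 | .685 | .812 |

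One set of assumptions comes near 138 with .33, the other with .385. N = 414 therefore does not identify the effect size used.

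**The case against.** The strongest reply is that nothing was miscalculated and an input was merely left out. The SAP says the conversion used SDs, in the plural, from prior studies, and one near 1.5% would give .33. The stated figures can even be made to yield it: the root-mean-square of the two change-score SDs is √((1.363² + 1.642²)/2) = 1.509, and 0.5/1.509 = .331. This possibility stands, and an undisclosed step is a real alternative to a wrong number. But the SAP describes no such pooling, and if a second SD was used, the statement that 1.3% determined power is incomplete. The text needs correcting either way.

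It is also fair to say that the near-matches to 138 are weak evidence. They depend on contrast and retention chosen together. Exchanging the retention patterns moves 136 to 123 in the first row (d = .33) and 134 to 129 in the second (d = .385). The first contrast ignores baseline, and the second assumes missing data at the enrolment visit. They serve here only to show that N does not settle which d was used.

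Finally, a consistent d alone would not make 414 checkable, because contrast, sidedness and retention are also missing. That is true, but those are reporting details. The mismatch between the stated inputs and the stated effect size remains.

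**Conclusion.** The concern holds. The stated difference and SD give d = .385 (.37 to .40 allowing for rounding of the SD), against .33 printed, and no SD that produces .33 appears in the documents. This rests on division alone and is firm.

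An error in N = 414 is not shown, and the mismatch does not by itself make the trial underpowered. The text ties 414 to d = .33. On that reading, the sample is conservative if 0.5% and 1.3% are right, and matched if the SD is about 1.5%. The unfavourable case needs .385 to have been entered and the SD to be near 1.5%; power at 138 per group would then be about 69% under the second set of assumptions in the table. The 26% scaling holds for any fixed contrast. The per-group sizes and powers in the table depend on the assumed contrast, two-sided .05 and retention pattern. The point should be corrected in the SAP, but it is not a reason to change the design.

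**What to change.** In the SAP, Power and Sample Size:

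- Confirm which d was entered in RMASS2, and correct whichever of the difference, SD or d is wrong so that the three agree.
- Cite the source of the SD, and say whether it is an SD of levels or of change. If SDs were pooled or converted, state the step.
- Keep N = 414, and restate its power for a 0.5% difference, or its detectable difference, with the agreed value.
- Give the time contrast, sidedness and retention pattern used, so that 414 can be checked.

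If an SD of 1.5% and d = .33 are confirmed as the values entered, only the 1.3% needs correcting and no re-run is needed. Otherwise the cost is SAP wording and, if the d entered changes, one RMASS2 run. Enrolment is unchanged.

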4. WRITTEN INFORMED CONSENT; ENROLLMENT AND RANDOMIZATION

Written Informed Consent and Enrollment:

Patients who are eligible and interested will be invited to an in-person, group-based, "Initial Visit," at which the study will be fully described, written informed consent will be obtained (Informed Consent document uploaded with this initial Study Application), and baseline self-report and clinical assessments will be performed. Approximate duration for this visit is 3 hours.

Randomization:

The study will apply a block randomization scheme, which will be computer-generated by the trial statistical consultant and administered by designated research staff. The study statistician will place assignments into sealed envelopes labeled with participant ID numbers. At the conclusion of the Initial Visit, the Project Manager will unveil group assignment. Laboratory staff who perform the clinical assays (primary study outcomes), data analysts, and research staff (with the exception of the Project Manager who will conduct randomization) will be blinded to group assignment.

At the conclusion of the Initial Visit, participants will be randomized to DD or DD-Me, delivered through automated text message, or telephonic communication, meet study staff (nurse, medical assistant [MA]), and receive training on intervention devices. All participants will continue to receive standard care at the clinic. Month-6 and month-12 assessments will be conducted at the same site. DD and DD-Me will be delivered between baseline and month-6 assessments, and are both intended to enhance the self-management support component of the Chronic Care Model (CCM).

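### Adjustment covariates are chosen by testing baseline balance and entered in an unstated form; as main effects only, they would leave most of a chance imbalance in the group-by-time effect

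*Combined protocol and SAP*

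**What the plan says.** The rule is in the SAP under Analytic Plan. It begins with a check on the randomisation: "Preliminary inferential statistical testing and effect size consultation will be used to determine if random assignment has resulted in statistical equivalence between groups". The consequence follows: "Significant covariates will be added to adjust for nonequivalence". The next words are a broken sentence that points to a second source of covariates: "Or variables related to missing data Multilevel models using full information maximum likelihood estimation".

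The model is then described: "Analyses will include the between-subjects factor treatment group and the within-subjects factor time". The target of inference is clear: "The cross-level group by time interaction effect will be of primary interest".

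The plan does not give the candidate variables, the significance level or effect-size cut-off for the balance check, or whether a covariate enters as a main effect or also interacts with time. It does not mention adjustment for baseline HbA1c.

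Two other places bear on this. The protocol's randomisation section says: "The study will apply a block randomization scheme". The assessments section gives three measurement occasions for HbA1c: "At baseline, month-6, and month-12 assessments, blood will be drawn at the clinic".

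**The concern.** There are two linked weaknesses.

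**Selection.** If block randomisation is carried out as planned, any baseline difference between arms is chance. A significance test therefore tests a hypothesis already known to be true, and a non-significant result does not show equivalence. A rule built on such tests picks variables by how unbalanced they happen to be. What makes a covariate worth adjusting for is how strongly it predicts the outcome. The primary model also becomes known only after baseline data have been inspected.

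**Form.** The stated interaction is group by time. A covariate that is constant over time and entered as a main effect shifts an arm's fitted mean equally at every visit, so it drops out of a comparison of changes between arms. On that reading, an analysis reported as adjusted for nonequivalence would carry nearly the same primary estimate as the unadjusted one. A real chance imbalance in baseline HbA1c would stay in the result.

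**Working it through.** **Inputs from the SAP (Power and Sample Size).** 138 per group; HbA1c SD 1.3; target 0.5 points; first-order autoregressive correlation .45, so lag two is .45² = .2025; missing data 15% per time point and 30% overall; "An alpha level of .05 and a power level of .80".

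**Assumptions.** Two-sided tests; .05 for the balance tests; baseline HbA1c is part of the outcome vector; time is a three-level factor. The documents state none of these.

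**1. The plan's own figures.** 3 × 138 = 414, and 414 × 0.70 = 289.8, the stated 290. The plan gives no figure for covariate adjustment, so there is none to reproduce.

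**2. Selection by chance.** P(at least one of k independent tests significant) = 1 − 0.95^k.
- k = 5: 23%
- k = 10: 40%
- k = 20: 64%

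**3. Why a main effect cancels with complete data.** For arm g and visit t, the fitted mean is ȳ(g,t) − γ·x̄(g), where x is the covariate and γ its coefficient. The month-12 change in arm g is [ȳ(g,12) − γx̄(g)] − [ȳ(g,0) − γx̄(g)] = ȳ(g,12) − ȳ(g,0). The term γx̄(g) has gone, whatever the imbalance.

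**4. Numerical check.** Simulations used 3 × 138 participants and the plan's SD and correlation.
- Complete data: the main effect changed the interaction by less than 2 × 10⁻¹⁴, under autoregressive and unstructured covariance.
- One complete dataset, month-12 interaction: −0.275 with no covariate, −0.275 with a covariate main effect, −0.275 with baseline HbA1c as a main effect, −0.175 with covariate-by-time, −0.102 with baseline HbA1c-by-time.
- Random loss at about 15%/30%: the main effect moved the month-12 estimate by about 0.02 points in mean absolute value, maximum about 0.09, against a standard error of about 0.215.

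Whether the cancellation does harm depends on the covariate. If its relation to HbA1c is the same at all visits, the change contrast is already free of its imbalance, and covariate-by-time terms move the estimate by almost nothing on average (−0.003). If its effect fades from 0.5 to 0 points per SD by month 12, an imbalance at the p = .05 threshold (1.96 × √(2/138) = 0.236 SD) shifts the contrast by 0.236 × 0.5 = 0.12 points. Only time-interaction terms remove that shift.

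**5. Baseline HbA1c, whose effect does fade under the plan's own correlation.**
- Difference just at p = .05: 1.96 × 1.3 × √(2/138) = 0.31 points.
- Conditional bias at month 6: 0.307 × (1 − .45) = 0.17.
- Conditional bias at month 12: 0.307 × (1 − .2025) = 0.24.

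These are about 34% and 49% of the 0.5-point target. For DD against the two DD-Me arms pooled (138 v 276), the figures are 0.27, 0.15 and 0.21. The plan's d = .33 implies an SD of 0.5/0.33 = 1.52; with it, the 138 v 138 figures rise by 1.52/1.3 = 1.17, to about 0.36, 0.20 and 0.29.

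**6. Precision available from baseline HbA1c.** Month 12, complete data, 138 v 138:
- Change contrast: SE = 1.3 × √(2 × 0.7975) × √(2/138) = 0.198. Power for 0.5 = Φ(0.5/0.198 − 1.96) = Φ(0.57), about 72%.
- Adjusted for baseline: SE = 1.3 × √(1 − .2025²) × √(2/138) = 0.153. Power = Φ(0.5/0.153 − 1.96) = Φ(1.30), about 90%.
- With 97 per group (138 × 0.70 = 96.6): about 56% and 78%.

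**7. Test-then-adjust against always adjusting.** For a covariate correlated .3 or .5 with the contrast (assumed), in a design with nominal 80% power:
- Overall size of test-then-adjust: .048 and .043.
- Power: .80 and .81, against .84 and .90 when always adjusting.
- When the imbalance lies at |z| 1.5 to 1.96 and is ignored: conditional type I error 7% to 10%.

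**The case against.** A reader might infer that the planned adjustment cannot change the primary effect at all. The documents do not support that, for three reasons.

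- The SAP says only that covariates are added. It does not exclude covariate-by-time terms, which do change the effect. Main effects only is the natural reading, but it is an inference.
- Exact cancellation needs complete data, and the plan expects 15%/30% loss with full-information maximum likelihood. Under random loss the shift is small. If dropout depends on the covariate in opposite directions by arm (a fairly strong assumption), the mean shift was 0.13 points at a covariate-outcome correlation of .3 and 0.22 at .5. The main effect then removed most of an unadjusted bias of −0.10 and −0.17.
- The broken sentence on missing-data variables signals that use. It is a legitimate route to covariates that does not depend on baseline testing, so it would also be wrong to say that chance alone decides the covariate set.

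The balance check also refers to effect sizes, so it need not be a strict p < .05 rule. That weakens the test-then-adjust figures, which assume one. It does not rescue the rule: without a cut-off it adds discretion, and an effect size for imbalance still says nothing about prognostic value.

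The protocol blinds data analysts to group assignment. This is a partial safeguard, but balance can be compared with coded arms, so the model would still depend on observed imbalance.

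Nor is there a type I error problem overall: simulated size is at or below .05. The 7% to 10% applies only within trials that have a particular imbalance.

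**Conclusion.** The point stands as a weakness of specification in the primary analysis that should be put right; it does not invalidate the trial. Covariates are selected on baseline imbalance and neither the set nor the form is fixed in advance. If they enter as main effects only, the adjustment does almost nothing for the effect of primary interest unless dropout is related to the covariate.

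The firmest figures concern baseline HbA1c, because they follow from the plan's SD and correlation: a threshold imbalance leaves a conditional bias of about a third of the target at month 6 and half at month 12. Leaving baseline HbA1c out of the model also gives up about 18 percentage points of month-12 power with complete data (72% v 90%).

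These results rest on the autoregressive correlation of .45, on baseline being in the outcome vector and on two-sided tests. The 40% to 64% depends on an assumed number of independent tests, and the gains from other covariates on assumed correlations that the documents do not give.

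**What to change.** Delete the baseline-testing rule and present baseline tables descriptively, without p-values. Before unblinding, state in the SAP:

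1. HbA1c models adjust for baseline HbA1c, either with months 6 and 12 as outcomes and baseline-by-time terms, or with a longitudinal model that constrains the baseline means to be equal across arms.
2. A short named list of prognostic covariates already collected (for example age, sex, comorbidities and medication use from the survey or health record) enters every model with covariate-by-time terms, whatever the observed balance.
3. Prespecified predictors of missingness are a separate set with their own stated purpose and form. This also repairs the broken sentence.

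The cost is about two sentences of SAP text, a few degrees of freedom out of 414 participants, and no new data.
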